6.5.5.1 Laboratory abnormalities

Incidence tables for the following laboratory abnormalities under Nivolumab treatment will be summarized:

- ALT or AST > 3 x ULN
- ALT or AST > 5 x ULN
- ALT or AST > 10 x ULN
- ALR or AST > 20 x ULN
- Total bilirubin > 2 x ULN
- ALP > 1.5 x ULN
- Concurrent (within 1 day after Nivolumab treatment) ALT or AST > 3 x ULN and total bilirubin > 2 x ULN
- Concurrent (within 30 days after Nivolumab treatment) ALT or AST > 3 x ULN and total bilirubin > 2 x ULN
- TSH value > ULN and
 - with baseline TSH value \leq ULN
 - with at least one FT3/FT4 test value < LLN within 2-week window after the abnormal TSH test
 - with all FT3/FT4 test values \geq LLN within 2-week window after the abnormal TSH test
 - with FT3/FT4 missing within 2-week window after the abnormal TSH test
- TSH < LLN and
 - with baseline TSH value \geq LLN
 - with at least one FT3/FT4 test value > ULN within 2-week window after the abnormal TSH test
 - with all FT3/FT4 test values \leq ULN within 2-week window after the abnormal TSH test
 - with FT3/FT4 missing within 2-week window after the abnormal TSH test

6.5.6 12-Lead ECG, QTc

Analyses of ECG and QTc will be performed on the SAF population.

Corrected QT (QTc) will be calculated using Bazett's (QTcB) and Fridericia's (QTcF) formula. If several assessments are performed on the same day (without timing information) the average of the values will be considered.

Descriptive statistics including arithmetic mean, SD, median, minimum, and maximum will be presented for the following ECG parameters: HR, RR, PR, QT, QRS, QTcB and QTcF. Parameters will be summarized for actual results and the change from baseline for the safety analysis set at each scheduled visit.

The number and percent of patients with absolute QTc interval prolongation or QTc increase from baseline will be defined and summarized. The criteria are:

- QTc prolongation: QTc interval > 450 msec, QTc interval > 480 msec and QTc interval > 500 msec.
- Increase from baseline in QTc interval: QTc interval increases from baseline > 30 msec and QTc interval increases from baseline > 60 msec.

The number and percent of patients with new clinically significant abnormalities on ECGs per the investigator's assessment at post-baseline time points will be summarized.

Unscheduled ECG data will be listed (Section 16 of the CSR) only.

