1.2 Schema

This study is composed of the following periods: Screening, treatment, active follow-up (FU), and long-term follow up. Participants will be considered “on study” during screening, treatment, active FU periods, and long-term FU periods. An overview of the study schema is presented in [Figure 1–1](#).

Figure 1–1: Study Schema

Abbreviations: C = cycle; D = day; EoT = End of treatment; FU = follow-up; i.v. = intra venous; LD = last dose; min = minute; q.d. = *quaque die* (once daily); Q4W = every 4 weeks

- a) Nivolumab 480 mg using a 30-min i.v. infusion every 4 weeks (Q4W). Regorafenib starting dose 80 mg orally every day (q.d.) for 21 days of each 28-day every 4 weeks (i.e. 21 days on, 7 days off). If starting dose is well tolerated (absence of any rash/HFSR any other or other Grade 2 or higher clinically significant toxicity) dose should be escalated to 120 mg orally daily starting with C2D1.
- b) Mandatory safety FU visit (at least 30 d after LD of regorafenib/nivolumab and 100 d after LD of nivolumab) and other active FU visits to collect safety and efficacy information for participants who discontinue study treatment without disease progression, if applicable.

Procedure	Screening		Treatment period ^a								EoT visit	Active FU		Long-term FU	Notes	
			Cycle1				Cycle 2			Cycle ≥3		30 d after LD of regorafenib and nivolumab ^b	100 d after LD for nivolumab ^b			
	within 28 d prior to first dose	within 7 d prior to first dose ^c	D 1	D 8	D15	D22	D1	D8	D15	D1	within 14 d after permanent discontinuation of regorafenib and nivolumab			every 3 months		
acceptable deviation				± 2 d			± 2 d			± 3 d		+ 7 d	+ 7 d	± 14 d		
AE review ^f	X	X	←=====→											Sections 8.3 and 10.3		
ECOG performance status	X	X	X				X			X	X	X	X		Section 8.2.5	
Serum pregnancy test if applicable (WOCBP only) ^g		X					X			X	X	X	X		Table 10–1	
Serology testing for Hepatitis B/C incl. HIV-1 (if applicable)	X		If clinically indicated													
Clinical chemistry ^h	X	X	X	X	X	X	X	X	X	X	X	X	X	X	Section 8.2.4	
Hematology	X	X	X	X	X	X	X	X	X	X	X	X	X	X	Table 10–1	
PT/INR and aPTT	X	X	X	If clinically indicated												
Urine analysis by dipstick ⁱ	X		X				X			X	X					
Thyroid function testing	X						X			X	X					
12-lead ECG	X										X			Section 8.2.3		
Vital signs (including weight)	X		X	X	X	X	X	X	X	X	X	X	X	Section 8.2.2		
Efficacy																
Tumor assessment (CT/MRI)	X									X	X	X	X	Section 8.1		
Survival status											X	X	X			

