5.4 Screen Failures

Screen failures are defined as participants who consent to participate in the clinical study but are not subsequently assigned to study intervention. A minimal set of screen failure information is required to ensure transparent reporting of screen failure participants to meet the Consolidated Standards of Reporting Trials (CONSORT) publishing requirements and to respond to queries from regulatory authorities. Minimal information includes demography, screen failure details and any serious AE (SAE).

Individuals who do not meet the criteria for participation in this study (screen failure) may be rescreened once. Whether the participant can repeat the screening will be discussed with the Sponsor. Sponsor's approval of re-screening for a participant must be documented.

Also, for re-screening, the participant has to re-sign the informed consent form, even if it was not changed after the patient's previous screening. The screening failure will be registered in Interactive Voice/Web Response System (IxRS) to close the participant identification number (PID), and re-screening will start again by signing a new informed consent form and being assigned a new PID via IxRS.

6. Study Intervention

Study intervention is defined as any investigational intervention intended to be administered to a study participant according to the study protocol.

Participants will receive nivolumab intravenously on day 1 of every cycle. Nivolumab will be administered as a dose of 480 mg using a 30-min i.v. infusion Q4W.

Regorafenib will be given orally every day for 21 days of each 28-day cycle. Each treatment cycle will be 28 days in duration. Regorafenib will be given as 40 mg tablets q.d. for 21 days of every 28-day cycle (i.e., 21 days on, 7 days off) as a starting dose of 80 mg. If starting dose of 80 mg daily is well tolerated (absence of any grade rash/HFSR or other Grade 2 or higher clinically significant toxicity) dose should be escalated to 120 mg orally daily starting with C2D1. Sponsor should be consulted, if the Investigator decides to not escalate the dose to 120 mg despite meeting the criteria.

When the two study drugs are administered on the same day, regorafenib is to be taken first orally followed by nivolumab infusion.

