6.4 Study Intervention Compliance

The administration of intravenous nivolumab will be performed in the clinic on D1 of every treatment cycle. The date and time of each infusion administered in the clinic will be recorded in the source documents and recorded in the electronic case report form (eCRF). Reasons for dose delay or infusion interruption will also be recorded in the source data and in the eCRF. The number of vials used will be recorded on the appropriate treatment dispensing form.

When participants are dosed at the site, they will receive regorafenib directly from the Investigator or designee.

Additionally, for treatment compliance oral administration of regorafenib will be done under supervision of site staff on PK visit days, and the dosing and time must be documented in the source data and eCRF on the following days: D1, D8 and D15 of C1, and on D1 and D15 of C2.

When participants self-administer regorafenib at home, compliance with regorafenib will be assessed at each study visit. Compliance will be assessed by counting returned tablets. A record of the number of regorafenib tablets dispensed to and returned by each participant must be maintained and reconciled with regorafenib start and stop dates, including dates for dose delays and/or dose reductions which will also be recorded in the eCRF. Any discrepancies between actual and expected amount of returned study medication must be discussed with the participant at the time of the visit, and any explanation must be documented in the source

records. An adequate record of receipt, distribution, and return/destruction of all study intervention must be kept.

CCI

CCI

CCI

CCI

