	If G3 hypertension recurs despite dose reduction and optimal antihypertensive therapy	Reduce another dose level or consider discontinuation ^a
G4	Discontinue	

Abbreviations: BP = blood pressure; CTCAE = common terminology criteria for adverse events; G = Grade; Hg = mercury

- a) If reductions are required resulting in regorafenib daily dose of less than 80 mg every other day, the regorafenib will be permanently discontinued. If toxicity returns to Grade 0-1 after dose reduction, dose reescalation is permitted in the subsequent cycle at the investigator's discretion. Subjects requiring a delay of >4 weeks should discontinue regorafenib treatment. However, continuation of regorafenib may be considered if, in the investigator's opinion, the patient may continue to benefit from the regorafenib treatment, and after consultation with Sponsor.

Table 6–6: Regorafenib Dose Modifications for Liver Function Test Abnormalities^a

Increases in AST/ALT/Bilirubin	Occurrence	Dose Interruption	Dose Modification (when resuming treatment)
(from baseline within normal limits) AST and/or ALT < 3 times ULN or total bilirubin < 1.5 times ULN	Any	Continue dosing	No Change
(from baseline AST/ALT more than 1 and up to 3 times ULN) AST or ALT more than 3 and up to 5 times the ULN	Any	Continue dosing	No Change
(from baseline within normal limits) AST or ALT more than 3 and up to 5 times the ULN or total bilirubin more than 1.5 and up to 3 times the ULN	1 st occurrence	Delay dosing until return to Grade \leq 1 or baseline	Reduce 1 dose level ^b
	Re-occurrence	Discontinue	
(from baseline any grade) AST or ALT more than 5 times the ULN or total bilirubin more than 3 times the ULN	1 st occurrence	Delay dosing until return to Grade \leq 1 or baseline	If the potential to reinstate regorafenib is considered to outweigh the risk of hepatotoxicity: reduce 1 dose level
	Re-occurrence	Discontinue	
(from baseline any grade)	Any	Discontinue	

Increases in AST/ALT/Bilirubin	Occurrence	Dose Interruption	Dose Modification (when resuming treatment)
AST and/or ALT > 20 x ULN			
AST and/or ALT > 3 x ULN with concurrent bilirubin > 2 x ULN	Any	Discontinue ^c	

Abbreviations: ALT=alanine aminotransferase; AST=aspartate aminotransferase; ULN = upper limit of normal

- For any of the events listed above (dose interruption or modification): monitor liver function tests weekly or more frequently until recovery to baseline or stabilization

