6.6.2.1 Nivolumab Treatment – Permanent Discontinuation

- Any Grade 2 drug-related uveitis, eye pain or blurred vision that does not respond to topical therapy and does not improve to Grade 1 severity within the re-treatment period OR requires systemic treatment
- Any Grade 3 non-skin, drug-related AE lasting >7 d or recurs, with the following exceptions for laboratory abnormalities, drug-related uveitis, pneumonitis, bronchospasm, neurologic toxicity, hypersensitivity reactions, infusion reactions, and endocrinopathies:
 - Grade 3 drug-related uveitis, pneumonitis, bronchospasm, neurologic toxicity, myocarditis, hypersensitivity reaction, or infusion reaction of any duration requires discontinuation
 - Grade 3 drug-related endocrinopathies, adequately controlled with only physiologic hormone replacement do not require discontinuation. Adrenal insufficiency requires discontinuation regardless of control with hormone replacement.
 - Grade 3 drug-related laboratory abnormalities do not require treatment discontinuation except:
 - Grade 3 drug-related thrombocytopenia >7 d or associated with bleeding requires discontinuation
 - Grade ≥ 3 drug-related AST, ALT or total Bilirubin requires discontinuation
 - Concurrent AST or ALT > 3 x ULN and total bilirubin > 2x ULN
- In most cases of Grade 3 AST or ALT elevation, nivolumab treatment will be permanently discontinued. If the investigator determines a possible favorable benefit/risk ratio that warrants continuation of nivolumab treatment, a discussion between the investigator and the Sponsor must occur.
- Any Grade 4 drug-related adverse event or laboratory abnormality (including but not limited to creatinine, AST, ALT, or Total Bilirubin), except for the following events which do not require discontinuation:
 - Grade 4 neutropenia ≤ 7 d
 - Grade 4 lymphopenia or leukopenia or asymptomatic amylase or lipase
 - Isolated Grade 4 electrolyte imbalances/abnormalities that are not associated with clinical sequelae and are corrected with supplementation/appropriate management within 72 hr of their onset

- Grade 4 drug-related endocrinopathy adverse events, such as, hyper- or hypothyroidism, or glucose intolerance, which resolve or are adequately controlled with physiologic hormone replacement (corticosteroids, thyroid hormones) or glucose-controlling agents, respectively, may not require discontinuation after discussion with and approval from the Sponsor.

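### SAP 6.5.5.1 times both concurrent liver rows from the nivolumab infusion, not between the ALT/AST and bilirubin elevations: the 1-day row cannot see 5 of the 7 draws in cycles 1-2, and the 30-day row leaves pairing undefined

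*SAP*

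**What the plan says.** SAP 6.5.5.1 lists laboratory abnormalities to be tabulated under nivolumab. Two rows combine transaminases with bilirubin: "Concurrent (within 1 day after Nivolumab treatment) ALT or AST > 3 x ULN and total bilirubin > 2 x ULN" and "Concurrent (within 30 days after Nivolumab treatment) ALT or AST > 3 x ULN and total bilirubin > 2 x ULN". In both, the parenthesis that qualifies *concurrent* is a time since nivolumab. The thyroid rows of the same list are timed from the test instead, for example "with at least one FT3/FT4 test value < LLN within 2-week window after the abnormal TSH test".

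The protocol uses the same liver thresholds twice, without reference to an infusion date. Section 6.6.2.1 (nivolumab discontinuation) has "Concurrent AST or ALT > 3 x ULN and total bilirubin > 2x ULN". Table 6-6 in section 6.6.1 (regorafenib) has "AST and/or ALT > 3 x ULN with concurrent bilirubin > 2 x ULN".

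Three other rules bear on the count:
- SAP 6.5.5 treats laboratory toxicities as treatment-emergent up to 30 days after the last regorafenib dose and 100 days after the last nivolumab dose.
- SAP 4.6 and 6.5.5 restrict unscheduled visits and unscheduled laboratory data to listings.
- Protocol 6.6.2 and 6.6.2.1 delay or stop nivolumab for drug-related liver abnormalities of specified grades.

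**The concern.** For a joint liver criterion, *concurrent* has to say how close in time the two elevations must be. The SAP gives a different quantity, the time since the last infusion, and leaves the first unstated. A programmer who follows the text builds a row that depends on when blood happens to be drawn relative to dosing. One who assumes the intended meaning departs from the SAP without a record.

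Safety of the combination is a secondary objective (Protocol Table 3-1), and these are the only rows in SAP 6.5.5.1 that join ALT/AST with bilirubin. The single-parameter rows cannot show whether both elevations occurred together in one participant. A participant with ALT 8 x ULN and bilirubin 3 x ULN on C1D15 would be absent from the 1-day row although both values come from one sample.

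**Working it through.** The plan states no count or rate for these rows, so there is no figure to reproduce. The check is how many scheduled draws each row can see.

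**Inputs**
- Infusions: "The administration of intravenous nivolumab will be performed in the clinic on D1 of every treatment cycle" (Protocol 6.4).
- Cycle length: "Each treatment cycle will be 28 days in duration" (Protocol section 6). Infusions therefore fall on days 0, 28, 56 and so on.
- Draws: the "Clinical chemistry" row of the Schedule of Activities gives C1 D1, D8, D15, D22; C2 D1, D8, D15; and D1 only from cycle 3. End-of-treatment and follow-up visits come in addition.
- ALT, AST and total bilirubin belong to the same panel (Protocol Table 10-1).
- Assumption: D1 blood and the infusion fall on the same date. The order of the two is not stated, so both orders are shown.

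**Lags at nominal dates.** D8, D15 and D22 are 7, 14 and 21 days after the infusion. With the ±2 d window, D8 is 7 − 2 = 5 to 7 + 2 = 9 days after. From cycle 3 the next in-cycle draw is the following D1, at 28 days.

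**Counts.** Over k cycles (k ≥ 2) there are 4 + 3 + (k − 2) = k + 5 scheduled draws. C1D1 has no earlier infusion, so if D1 blood comes first there are k + 4 post-infusion draws.

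| Cycles k | All draws (k + 5) | 1-day row, D1 blood before infusion | 1-day row, same-day draw counts as day 0 | 30-day row, D1 blood before infusion |
|---|---|---|---|---|
| 2 | 7 | 0 of 6 | 2 of 7 | 6 of 6 |
| 6 | 11 | 0 of 10 | 6 of 11 | 10 of 10 |
| 24 | 29 | 0 of 28 | 24 of 29 | 28 of 28 |

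**1-day row.** Under either order, C1 D8, D15, D22 and C2 D8, D15 cannot qualify: 5 of 7 draws in cycles 1-2. If same-day draws count, C1D1 should still be set aside, because SAP 6.5.5 takes the last value before or on the first dosing day as baseline. That leaves (k − 1) of (k + 4): 1 of 6, 5 of 10 and 23 of 28. These remaining D1 draws are also selected. They count only if an infusion is given that day, and Protocol 6.6.2 and 6.6.2.1 would generally withhold it from a participant whose drug-related qualifying values are already known.

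**30-day row.** The largest nominal lag is 28 days, so every scheduled draw during 4-weekly dosing is inside. A cycle ≥ 3 D1 visit at the full +3 d lies 28 + 3 = 31 days after the previous infusion and falls just outside if blood is drawn first. Days 31 to 100 after the last infusion are excluded, although SAP 6.5.5 counts them as treatment-emergent for nivolumab. When nivolumab was the last drug given, the 30-day follow-up visit (+7 d) falls at days 30 to 37, so only a draw on day 30 itself qualifies.

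**Unscheduled tests.** The footnote to Table 6-6 calls for liver tests at least weekly after the listed events. From cycle 3 the schedule has no weekly slots, so such samples would be listed but not tabulated. They cannot fill the gap in the 1-day row.

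**After re-anchoring.** Because the three analytes share a panel, every post-baseline scheduled draw can contribute to both rows, for example 10 of 10 over six cycles.

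**The case against.** A reader might infer that the joint liver-injury count is near zero by construction. The documents do not support that. The 30-day row sees all scheduled draws at nominal 4-weekly dosing, and the C1D15 example, 14 days after infusion, is counted there. For the 1-day row, emptiness depends on D1 blood preceding the infusion. SAP 4.6 describes timing by relative day, so same-day draws may well count. An end-of-treatment visit soon after an infusion could also supply a draw.

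It can also be argued that the 30-day row keeps the word *concurrent*, which may be read as simultaneous elevations occurring within 30 days of nivolumab. That is a fair reading. What stands is that no limit is stated, so peaks from different dates could be paired; it is not shown that they would be.

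The list concerns abnormalities under nivolumab, so events on regorafenib alone long after the last infusion are arguably out of its scope. The narrower point survives: 30 days is shorter than the SAP's own 100-day nivolumab window.

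Finally, other outputs overlap. ALT/AST and bilirubin have single-parameter rows without a day limit, worst-grade tables use the full treatment-emergent period, high bilirubin and high liver enzymes are AEs of importance, and all data are listed. This limits the harm to the joint tabulation. It does not make the stated definition correct.

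**Conclusion.** Wrong as written, of moderate weight. Both rows are anchored on the infusion and omit the interval that *concurrent* needs. The 1-day row excludes 5 of the 7 scheduled draws in cycles 1-2 whatever the draw order. It has no eligible scheduled on-treatment draw if D1 blood precedes the infusion, and is still selectively low if same-day draws count. The 30-day row is broadly inclusive during on-schedule dosing, but leaves pairing unstated and loses days 31-100.

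These statements rest on nominal visit dates and on D1 blood and infusion sharing a date. How many participants would be missed cannot be computed. A reader might go further and infer that the hepatotoxicity signal is lost or that phase III planning would be misled. The documents do not support this: the safety endpoint is AE incidence and severity, the single-parameter outputs remain, and the planned early data look covers response only (SAP 4.4). The primary endpoint is unaffected.

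**What to change.** In SAP 6.5.5.1, replace the two rows with: *total bilirubin > 2 x ULN within 1 day (second row: 30 days) of an ALT or AST > 3 x ULN*. In the same edit:
- state whether the window runs forward only from the ALT/AST elevation or in both directions;
- count events from first dose to the end of the laboratory treatment-emergent period in SAP 6.5.5 (30 days after last regorafenib, 100 days after last nivolumab);
- include unscheduled liver tests in these two rows, as a stated exception to SAP 4.6 and 6.5.5. Without this, off-schedule monitoring stays out of the table even after rewording.

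The cost is a few lines of SAP text and a minor program change, with no new data collection. The reported count may rise.

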6.5.7 ECOG status

The ECOG performance status will be summarized by descriptive statistics tables over time, incl. change from baseline. Two sets of tables will be produced, interpreting the score as categorical variable (categories 0-5) as well as continuous variable.

6.5.8 Other safety measures

Vital signs (i.e. blood pressure, heart rate, weight and BMI) will be tabulated and summarized by visit for observed values and changes from baseline using descriptive statistics, as appropriate.

Unscheduled vital signs data will be listed (Section 16 of the CSR) only.

7. Document history and changes in the planned statistical analysis

This is the first amendment of the SAP.

CCI
